3 STUDY DESIGN

MS-SMART is a multicentre, multi-arm, double blind, placebo-controlled phase IIb randomised controlled trial. A total of 440 patients with SPMS, with an entry criteria of an EDSS score of 4.0-6.5 will be equally randomised to receive placebo or one of the three active agents (amiloride 5mg bd, riluzole 50mg bd and fluoxetine 20mg bd). Patients will be followed up for 96 weeks with outcomedata collected after 0, 24, 48 and 96 weeks (see flowchart below). That is, the duration of the trial for a trial participant is 96 weeks (a telephone assessment at week 100, 4 weeks post completion will be conducted). This is standard practice for phase II trials in SPMS.

4 STUDY POPULATION

4.1 NUMBER OF PARTICIPANTS

440 adult patients (male and female) will be recruited into MS-SMART across at least 10 UK sites over a one year recruitment period.

4.2 INCLUSION CRITERIA

- Confirmed diagnosis of SPMS. Steady progression rather than relapse must be the major cause of increasing disability in the preceding 2 years. Progression can be evident from either an increase of at least one point in EDSS or clinical documentation of increasing disability in patients notes
- EDSS 4.0-6.5
- Aged 25 to 65 inclusive
- Women and men with partners of childbearing potential must be using an appropriate method of contraception to avoid any unlikely teratogenic effects of the 3 drugs from time of consent, to 6 weeks after treatment inclusive
- Women must have a negative pregnancy test within 7 days prior to the baseline visit unless not of child bearing potential (e.g. have undergone a hysterectomy, bilateral tubal ligation or bilateral oophorectomy or they are postmenopausal)
- Willing and able to comply with the trial protocol (e.g. can tolerate MRI and fulfils the requirements for MRI, e.g. not fitted with pacemakers or permanent hearing aids) ability to understand and complete questionnaires
- Written informed consent

4.3 EXCLUSION CRITERIA

- Pregnancy or breast feeding females
- Baseline MRI scan not of adequate quality for analysis (e.g. too much movement artefact)
- Significant organ co-morbidity (e.g. malignancy or renal or hepatic failure)
- Relapse within **3 months** of baseline visit
- Patients who have been treated with iv or oral steroids for an MS relapse/progression
- within **3 months** of baseline visit (these patients can undergo future screening visits once the 3 month window has expired), patients on steroids for another medical condition may enter as long as the steroid prescription is not for multiple sclerosis (relapse/ progression)..
- Use of Simvastatin at 80mg dose within **3 months** of baseline visit (lower doses of Simvastatin and other statins are permissible)
- Commencement of fampridine within **6 months** of baseline visit

- Use of immunosupressants (e.g. azathioprine, methotrexate, cyclosporine) or first generation disease modifying treatments (β-interferons, glatiramer) within 6 months of baseline visit
- Use of fingolimod/fumarate/teriflunomide/laquinomod/or other experimental disease modifying treatment (including research in an investigational medicinal product) within 12 months of baseline visit
- Use of mitoxantrone/natalizumab/alemtuzumab/daclizumab if treated within **12 months** of baseline visit
- Primary progressive MS
- Relapsing-remitting MS
- Known hypersensitivity to the active substances and their excipients to any of the active drugs for this trial
- Use of an SSRI within 6 months of the baseline visit
- Current use of tamoxifen
- Current use of herbal treatments containing St. John's Wort
- Patients with a history of bleeding disorders or currently on anticoagulants
- Use of monoamine oxidase inhibitors, phenytoin, L-tryptophan and/or neuroleptic drugs within **6 months** of the baseline visit
- Use of: lithium, chlorpropamide, triamterene, spironolactone, within **6 months** of the baseline visit
- Current use of potassium supplements
- Significant signs of Depression
- Bipolar disorder
- A Beck Depression Index score of 19 or higher
- Epilepsy/seizures
- Receiving or previously received Electroconvulsive therapy treatment
- Glaucoma
- Routine screening blood values (LFT) >/ 3 x upper limit of normal (ULN) of site reference ranges (AST/ALT, bilirubin, ^xGT)
- Potassium <2.8mmol/l or >5.5mmol/l
- Sodium <125mmol/l
- Creatinine >130µmol/l
- WBCs <3x10⁹/I
- Lymphocytes <0.8 x 10⁹/l
- Neutrophil count <1.0 x10⁹/l
- Platelet count <90 x10⁹/l

Sponsor No.12/0219 v7 Page **33** of **73** • Haemoglobin <80g/l

4.4 Participation in Other Trials

Whilst on study, MS-SMART trial participants cannot take part in other clinical trials of Investigational Medicinal Products (or devices) until 6 weeks after finishing MS-SMART trial medication and/or final assessments. Participation in other research while taking part in MS-SMART is permissible.

5 PARTICIPANT SELECTION AND ENROLMENT

5.1 IDENTIFYING PARTICIPANTS

Initial Identification

There are several potential routes of initial identification:

- In clinics run by PIs or their associate neurologists at participating sites
- In clinics run at other MS centres/neuroscience/hospital centres, where they will be set up as Participant Identification Centres [PICS]. All referrals will require medical history records confirming MS and other relevant medical conditions from referring centres
- Using existing MS Research Databases and other databases such as SHARE, which contain the contact details of people who have expressed a wish, and consented, to be contacted directly when a study they may be suitable for is recruiting
- By General Practitioners (GPs) at routine appointments
- By self-referral from potential participants who may be made aware of the project by people who have already taken part in the study, via trial publicity events/literature or have seen the study on MS charities web-sites or been approached about it

Depending on the route of identification several processes may then be used to follow up their suitability as a participant including:

- Patients may be briefed in clinic about the study directly by a member of the clinical team; and also to ensure that the patient is likely to fulfill the general criteria to enter the trial. Patients will be given a Patient Information Leaflet
- Patients may receive an initial telephone contact from a research nurse, to explain the trial and to ensure that the patient is likely to fulfill the general criteria to enter the trial. Patients will be sent a PIL
- After a period of *at least* 24 hours after receiving the Patient Information Leaflet, the patient will be contacted again and invited for an informed consent, screening visit if they would like to proceed with the study

If required and following documented permission from the patient, their consultant / general practitioner will be contacted to provide written confirmation of the patient's medical status for use in confirming the patient's medical history for assessing eligibility. This will take place prior to the screening visit and will avoid, for example, unnecessarily bringing patients who live some distance from the clinic in for the screening visit.

*- (see below).

*A log of all patients with whom contact has been made (following receipt of the PIL) will be kept (see below).

Sponsor No.12/0219 v7 Page **34** of **73**

5.2 CONSENTING PARTICIPANTS

This will occur at the screening visit. All persons involved in obtaining consent at sites must be delegated this task by the Chief Investigator/Principal Investigator and that this delegation must be documented in the delegation log.

Patients will be invited in for an informed consent visit with an appropriately experienced, qualified and Good Clinical Practice (GCP) trained member of the study team who will go through the PIS with them (explaining the aims, methods, anticipated benefits and potential hazards of the study). The patient will be given an opportunity to ask further questions. It will be explained that they are under no obligation to consent to the trial and that they can withdraw at any time during the trial without providing a reason. If they are then still willing to participate they will be asked to give their written consent. This written consent will be witnessed by the investigator who will also sign and date. It is the Principal Investigators responsibility to ensure that written informed consent is obtained from all participants before any study procedures are undertaken. They will then proceed to screening. A copy of the consent form will be given to the participant and the original copy will be retained at the study site.

Patients unable to consent for themselves due to language barriers will have access to the usual translation services provided by the site, to accommodate patient needs.

If new safety information results in significant changes in the risk/benefit assessment, the participant information sheet and consent form will be reviewed and updated if necessary. All participants, including those already being treated, will be informed of any new information, be given a copy of the revised information sheet and will be re-consented as appropriate.

5.3 SCREENING FOR ELIGIBILITY

Only individuals who are NHS employees (substantive or honorary) and who have access permissions will examine hospital and research databases for potentially eligible participants. This will be documented in the delegation log.

Once written informed consent has been obtained, trial participants will follow the trial pathway as outlined in section 7.2.

The patient's consultant / general practitioner will be sent confirmation that their patient has consented to enter the trial and further details about the trial. The consultant/GP will be asked to provide written confirmation of the patient's medical status for use in confirming the patient's medical history for assessing eligibility.

5.4 INELIGIBLE AND NON-RECRUITED PARTICIPANTS

Each MS-SMART recruiting site will be required to maintain an anonymised log of all patients who are ineligible for the trial and all eligible patients who, when approached about the trial, are not randomised because they decline participation. This information will allow generalisation of the trial results in accordance with CONSORT reporting guidelines.

Annoymised information will be collected including:

- age
- gender
- date screened
- AND

MS-SMART Version 7 4th June 2018

- Reason not eligible for trial participation
- 0R
- Reason for declining participation despite eligibility
- 0R
- Other reason for non-registration

5.5 RANDOMISATION

5.5.1 Randomisation Procedures

MS-SMART is a double blind trial with additional blinded assessment of secondary and exploratory mechanistic outcome measures. Randomisation will be performed by the research nurse via a secure web-based randomisation service (ECTU) on a 1:1:1:1 basis employing the following minimisation variables:

- sex
- age (<≥ 45yrs)
- baseline EDSS (4.0-5.5; 6.0-6.5)
- site

The minimisation algorithm will incorporate a random element to maintain unpredictability of treatment allocation.

To ensure that treatment allocation remains concealed to both staff and participants, the following measures will be taken:

- Fluoxetine, amiloride and riluzole will be over-encapsulated so they are identical in appearance and the same placebo for fluoxetine, amiloride and riluzole will be used. The fluoxetine/amiloride/riluzole placebo will be identical in appearance in order to disguise the identity
- The same number of the capsules will be prescribed for participants in each arm
- The drugs supplied from the manufacturers will be re-packaged by an organisation independent of the trial and the same organisation will supply pharmacies at participating sites directly with the trial drugs
- Drug supplies to pharmacies will be coded
- The randomisation list will be held by the ECTU to ensure that treatment allocation is concealed from the investigator's team and the participant, whilst providing provisions for emergency un-blinding. Details of the randomisation process will be available in the Investigator Site File (ISF). The identities of the co-ordinating staff whose roles in the trial require them to have access to treatment allocation codes will be recorded in the trial master file (TMF)

The randomisation system will be web-based and require a personal log-in and password. Only those individuals who have attended the site-initiation visit, are trained and are in the delegation-log can carry out this process.

Once a patient has been randomised they will be given a card to indicate they are on the trial with the emergency contact numbers for medical advice. Participants will be instructed to show this card to any healthcare professional involved in their care who is not involved in the trial. Any trial participant who withdraws from the study will not be replaced.
Emergency Un-blinding Procedures

Un-blinding may take place in situations where the safe management of the participant's medical condition necessitates knowledge of the study medication by the person(s) responsible for the participant's care. Where possible, members of the local research team should remain unblinded.

If unblinding is required the local PI/other medical staff should contact ECTU in the first instance via telephone on [name] during normal working hours (Monday to Friday 9am to 5pm). The call will then be relayed to one of the co-CIs, [name] or [name] (or their designated deputy) for medical guidance. Out of hour calls will be diverted to the designated CI (or deputy).

The person requesting the unblinding will provide details including the protocol number and trial name, name of the requester, reason for unblinding, patient name, participant number and timeline to receive the unblinded information. If knowledge of the treatment allocation is required in order to treat the patient, the code break number will be given to the local Pl/other medical staff requesting to unblind the patient. The local Pl/other medical staff can then use the code break number to reveal the participants treatment allocation. In this way, the treatment will be unblinded at the local site but not to the ECTU member of staff or CIs.

- The local PI/ medical staff will deal with the medical emergency (upon receipt of the treatment allocation revealed by the code break number)
- Details of the code break will be documented on the code break form and filed in the local Site File
- Code breaks will also be documented at the end of the study in the statistical report.
- The CI/ investigator team will notify the Joint Research Office for the UCL sponsor (JRO) of a code break and provide details of the necessity to un-blind
- The CI/PI will also notify trial committees (in accordance with their charter)

The following procedure will be used to un-blind for the submission of a SUSAR report to the regulatory agencies:

- ECTU will hold the code break list during normal working hours (Monday Friday, 9am to 5pm)
- A member of the JRO sponsor's office will contact the ECTU during normal working hours via telephone on [name] in the first instance, requesting unblinding information from the randomisation list
- ECTU will provide their email address and name for the request to be formalised in an email
- The sponsor will provide in the email the protocol number and trial name, name of the requester, reason for unblinding, patient name, participant number and timeline to receive the unblinded information
- The sponsor will provide the unblinded information on the e-SUSAR website
- This information will not be forwarded to the trial team and will be kept in the JRO sponsor file

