Multiple sclerosis (MS) is a disabling and progressive neurological disease that affects approximately 100,000 people in the UK. Many patients with MS experience two phases of disease; early MS (also called relapsing remitting MS, RRMS) and late MS (also called secondary progressive MS (SPMS). Early MS is due to inflammation of the nerves and the insulation (called myelin) that surrounds the nerves. Early MS is often characterised by periods of "attacks" interspersed with periods of "remission" with no or low disease symptoms. Late or progressive MS, which affects the majority of patients and typically emerges after 10-15 years of disease, results from actual nerve death (also called neurodegeneration). The progressive stage of disease results not in individual attacks but slow, cumulative and irreversible disability affecting walking, balance, vision, cognition, pain control, bladder and bowel function. Critically, and unlike early disease, there is no proven treatment for the late stage of MS. This is therefore an urgent and major unmet health need. MS-SMART directly addresses this need and will evaluate in this clinical trial three drugs (fluoxetine, riluzole or amiloride), all of which have shown some promise in MS, and in particular in SPMS. The trial is randomised and blinded. Randomisation means patients can get any one of the three active drugs or the inactive placebo/dummy; blinded means that neither patients nor the doctors will know which drug or placebo patients are receiving. Randomisation and blinding are standard approaches in clinical trials to ensure unbiased testing of drugs. All patients in MS-SMART will have periodic MRI (magnetic resonance imaging) brain scans and after 96 weeks these will be analysed. We will then compare the scans of each drug to the placebo or dummy to see if any of the drugs slow the rate of brain shrinkage that normally occurs in SPMS. This measured change in brain size is the primary (major) outcome of MS-SMART.

STUDY TITLE	MS-SMART: M ultiple S clerosis- S econdary Progressive M ulti- A rm R andomisation T rial
	A MULTI-ARM PHASE IIB RANDOMISED, DOUBLE BLIND PLACEBO-CONTROLLED CLINICAL TRIAL COMPARING THE EFFICACY OF THREE NEUROPROTECTIVE DRUGS IN SECONDARY PROGRESSIVE MULTIPLE SCLEROSIS.

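### The emergency un-blinding procedure says the local research team should stay unblinded, almost certainly a slip for blinded, and no other sentence limits sharing of the allocation within the site

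*Protocol*

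**What the plan says.** Section 5.5.1 sets the rule for the trial: "MS-SMART is a double blind trial with additional blinded assessment of secondary and exploratory mechanistic outcome measures". It introduces its measures with the purpose "To ensure that treatment allocation remains concealed to both staff and participants". It has the trials unit (ECTU) hold the randomisation list so that "treatment allocation is concealed from the investigator's team and the participant, whilst providing provisions for emergency un-blinding". The Lay Summary puts it more simply: "blinded means that neither patients nor the doctors will know which drug or placebo patients are receiving".

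The Emergency Un-blinding Procedures (5.5.2 in the contents list) open by allowing a code break only where safe management "necessitates knowledge of the study medication by the person(s) responsible for the participant's care". The next sentence is the one at issue: "Where possible, members of the local research team should remain unblinded". The section then describes the request to ECTU, the relay to a co-chief investigator for medical guidance, and the release of a code break number to the requesting local investigator or medical staff. It concludes: "In this way, the treatment will be unblinded at the local site but not to the ECTU member of staff or CIs".

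**The concern.** Read literally, the sentence tells a site to leave its research team unblinded whenever it can, which is the opposite of what a double-blind trial requires. It is body text of the current version 7, it is complete and grammatical, and it sits in the section that a site would consult during a code break.

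The stake is knowledge spreading beyond the clinician who needs it. Site staff make several judgements that knowledge of the allocation could influence: causality of adverse events, dose reduction and re-challenge, and EDSS. If the allocation of a code-broken participant became known across the local team, those judgements could be affected for the rest of that participant's follow-up, up to week 96.

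**Working it through.** No arithmetic applies. The check is to compare the sentence with every other statement on blinding, and then to ask what it governs that nothing else does.

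**1. Direction of the other statements.**
- Lay Summary: patients and doctors do not know the allocation.
- Section 5.5.1: double blind; secondary and mechanistic outcomes assessed blind; allocation concealed from staff, and specifically from the investigator's team.
- The sentence before the one at issue: un-blinding is tied to clinical need and to those responsible for care.
- SUSAR un-blinding, later in the same section: the information is kept in the sponsor's file and is not passed to the trial team.

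All point the same way, and nothing corrects or explains the exception.

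**2. What the sentence must have meant.** People can only remain in a state they are already in. Under section 5.5.1 the local team is blinded before a code break. The qualifier about possibility also makes sense only as a limit on disclosure. The intended word is almost certainly *blinded*.

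**3. What the sentence alone governs.** Three questions arise at a code break:
- *When may a code be broken?* Answered elsewhere: when safe management requires it.
- *Who receives the code?* Answered elsewhere: the requesting local investigator or medical staff, if the allocation is needed to treat. ECTU staff and the chief investigators are shielded by the mechanism.
- *Who else at the site may then be told?* Only this sentence addresses it, and it is inverted. The later statement that treatment is unblinded at the local site does not narrow it. The code break form is filed in the local Site File, with no access restriction stated in that section.

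**4. Do code-broken participants stay in the data?** They can. Section 5.5.3 says that stopping study drug is not necessarily withdrawal and asks for follow-up, including the 96-week MRI. Section 10.9 provides both for un-blinding after an overdose with clinically significant symptoms and for the patient continuing in the trial. Section 6.5 makes the primary analyses intention-to-treat.

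**5. Which assessments could be affected?**
- *Adverse-event causality:* a clinical decision by the investigator (10.4, 10.4.2), to be made as though the participant were on active drug. Knowing the allocation makes that convention harder to keep.
- *Dose reduction and re-challenge:* largely at the local investigator's discretion (6.4).
- *EDSS:* scored by the assessing physician. The schedule in 7.2 lists an independent assessing neurologist at weeks 0, 48 and 96, separate from the treating neurologist. At weeks 48 and 96, however, a nurse may score it by telephone, and the text does not say that this nurse must be someone other than the study nurse listed at the clinic visits.
- *Relapse grade:* defined in 10.4.6.1 by corticosteroid treatment and hospital admission, so less open to the rater's expectation.
- *PBVC:* an automated registration method (2.2.1), so little exposed.

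**The case against.** The strongest reply is that this is a self-evident typing error which no trained site would follow. Section 5.5.1 is unambiguous, the verb shows what was meant, and the protocol offers no evidence that any site acted on the literal words. That is a good reason to rate the point low. It is not a reason to leave an inverted instruction in operative text.

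Three stronger readings are tempting, and the documents do not support them.

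- *That this sentence is the only safeguard on who learns the allocation.* It is not. The procedure also has the need-to-treat condition, the call relayed to a co-chief investigator, a named requester with a stated reason, release of the code only to that requester, the code break form, notification of the sponsor and trial committees, and listing of code breaks in the statistical report. What remains uncovered is onward sharing afterwards.
- *That the team managing the participant also rates the EDSS.* The schedule separates the treating from the assessing neurologist. The remaining exposure is the assessor being told, or a nurse scoring by telephone.
- *That a count of affected participants can be given.* Assuming code breaks in 1–3% of 440 participants would give 0.01 × 440 = 4.4 to 0.03 × 440 = 13.2. The protocol states no such rate, and using that count as the number followed by an unblinded team would further assume that every code break spread to everyone. The requesting clinician is meant to know under either wording.

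It is also fair to say that little prospective benefit is left. Section 1.2.2.1 records that recruitment is complete, version 7 is dated 4 June 2018, and the synopsis ends the trial on 31 October 2018.

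**Conclusion.** The sentence is wrong as written. It contradicts the Lay Summary and section 5.5.1, and it reverses the only guidance on sharing an allocation within a site after a code break.

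The consequence is limited and conditional. It concerns code-broken participants only, because the randomisation list stays with ECTU and supplies are coded and over-encapsulated, so the sentence gives no route to anyone else's allocation. Among those participants it matters where three things hold: the site follows the literal words, the participant stays in follow-up, and someone who makes a judgement-based assessment is told. It could then bias adverse-event causality, dose decisions and EDSS. The documents do not show that this happened, and without a number of code breaks no size can be put on it. A threat to the primary PBVC comparison should not be inferred.

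This is a lower-severity correction, not one on which the validity of the trial turns.

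**What to change.** In the Emergency Un-blinding Procedures, change *unblinded* to *blinded* in the sentence on the local research team. Add one sentence stating that, after a code break, the allocation is known only to the clinician or clinicians who need it to treat the participant, and is not passed to the assessing physician or to other staff who collect outcomes, including any nurse who scores EDSS by telephone. Make the later statement that treatment is unblinded at the local site agree with this.

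Because recruitment is complete, the sponsor should also check the existing code break forms for any case in which an outcome assessor learned the allocation, and note such cases where code breaks are reported in the statistical report.

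The cost is a one-word correction, one added sentence with a matching edit, a note to sites and a short review of forms already held. Sample size and the analysis model are unaffected.
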